2.3. Benefit/Risk Assessment

More detailed information about the known and expected benefits and risks and reasonably expected adverse events of mepolizumab may be found in the Investigator's Brochure, Participant Information Leaflet, Prescribing Information.

209682

TMF-14888313 CONFIDENTIAL

2.3.1. Risk Assessment

Potential Risk of	Summary of	Mitigation Strategy
Clinical	Data/Rationale for Risk	guton somegj
Significance		
Investigational Prod	duct (IP) (mepolizumab)	
Systemic Reactions (Allergic [type I hypersensitivity] and Other systemic reactions) including Anaphylaxis	There have been reports of systemic reactions (including hypersensitivity reactions, such as anaphylaxis, bronchospasm, angioedema, rash, urticaria and hypotension) with mepolizumab. These are usually acute, occurring within a few hours of the drug being administered, but can also be delayed, occurring after several days	Safety monitoring of participants will occur during SC administration and for one hour after the end of injection for the first 3 injections, then per institutional guidelines. Such monitoring will include general safety monitoring will include general safety monitoring including monitoring for both systemic reactions (Allergic [type I hypersensitivity] and Other systemic reactions) and local site reactions. In the event of an acute severe reaction (e.g., anaphylaxis) following administration of study treatment, there must be personnel/staff onsite at the treatment facility who are appropriately trained in basic life support to manage the patient including administration of medications (e.g., epinephrine), and have access to a system that can promptly transport the patient to another facility for additional care if appropriate. Customised AE and SAE case report form (CRF) utilised for targeted collection of information for systemic reaction adverse events. Use of Joint National Institute of Allergy and Infectious Diseases (NIAID)/Food Allergy and Anaphylaxis Network (FAAN) 2nd Symposium on Anaphylaxis to collect data on reports of anaphylaxis (see Appendix 7).

Potential Risk of Clinical Significance Study Procedures	Summary of Data/Rationale for Risk	Mitigation Strategy
There are few invasive procedures such as blood collection for chemistry assessment in which blood will be collected from peripheral veins. Also, ECG assessment will be conducted.	Fainting associated with needle prick and contact dermatitis because of jelly applied before ECG assessment	The participants have been informed about the all the study procedures and invasive procedure for e.g. blood collection during informed consent process. No further risk mitigation strategy is required.
COVID-19 pandem	ic	
COVID-19 pandemic	The COVID-19 pandemic may impact the conduct of clinical studies. Challenges may arise from quarantines, site closures, travel limitations, interruptions to the supply chain for the investigational product or other considerations if site personnel or study participants become infected with COVID-19. These challenges may lead to difficulties in meeting protocol-specified procedures.	Missing protocol required data/visits due to COVID-19 should be noted in participant notes and recorded as a COVID-19 protocol deviation. Visits that were conducted via the telephone will not be classified as missed visits, however missed assessments (e.g. spirometry) should be recorded as COVID-19 protocol deviations. The study CRF will capture information on probable, suspected or confirmed COVID-19 infections. Additionally, a further targeted CRF page will capture the frequency of missed or partially completed study visits or assessments due to the COVID-19 pandemic. Home healthcare visits (home visits and telemedicine visits) may be implemented for scheduled visits from Visit 3 onwards for participants unable to attend a site visit due to COVID-19 related restrictions. Intercurrent events related to the COVID-19 pandemic (such as quarantines, site closures or other related issues) will be accounted for

Potential Risk of Clinical	Summary of Data/Rationale for Risk	Mitigation Strategy
Significance		
		within the analysis of the study.

2.3.2. Benefit Assessment

During the entire duration of the study, all the participants will receive medicines such as mepolizumab, OCS (as needed) and ICS plus LABA combination free of cost. Also, all the routine procedures, which are offered as standard of care for Asthma evaluation (for e.g. Spirometry assessment) and safety assessment (ECG, chemistry) will be provided free of cost.

Multiple clinical studies (MENSA, SIRIUS, COSMOS) have shown that mepolizumab has significantly reduced clinically significant annual asthma exacerbation rate and improved lung function in patients with severe eosinophilic asthma. SIRIUS study demonstrated that in patients requiring daily oral glucocorticoid therapy to maintain asthma control, mepolizumab had a significant glucocorticoid-sparing effect.

2.3.3. Overall Benefit: Risk Conclusion

[figure not shown]
The benefit: risk of mepolizumab 100mg SC every 4 weeks in the approved indication of severe eosinophilic asthma is positive.

3. OBJECTIVES AND ENDPOINTS

Objectives	Endpoints
Primary	*
To evaluate the safety, and tolerability of mepolizumab in participants with severe refractory asthma with elevated eosinophils	The primary estimand will be defined by the following: Endpoints: Incidence of on-treatment adverse events (AEs), serious adverse events (SAEs) and adverse events of special interest (AESIs)
	 Summary measure: Counts and percentages for incidence of at least one AE will be summarised overall, by system organ class and by preferred term
	 Population of interest: Severe refractory asthma patients in India with elevated eosinophils
	Key intercurrent events:Discontinuation of treatment (for any reason)
	 Strategy for intercurrent events: While on-treatment strategy will be used for treatment discontinuation. This will estimate the percentage of participants experiencing an AE, while receiving treatment. AEs will be defined as on-treatment between the first dose up to and including 28 days following the last dose of mepolizumab.
	A supplementary estimand will be defined using identical properties as for the primary estimand (summary measure, population of interest and key intercurrent events), however this supplementary estimand will report all AEs regardless of the discontinuation of study treatment. Endpoints: Incidence of AEs and SAEs
	 Strategy for intercurrent events: Treatment policy strategy will be used for treatment discontinuation. This summary will therefore be inclusive of all on-treatment and post-treatment AEs.
Secondary	
To evaluate the efficacy of mepolizumab in participants	The following secondary estimand is defined by the following:

Objectives	Endpoints
with severe refractory asthma	Endpoints:
with elevated eosinophils	 Number of clinically significant exacerbations (including exacerbations requiring hospitalization or ED visits) Number of exacerbations requiring hospitalization or ED visits Number of exacerbations requiring hospitalization Summary measure: Rate ratio comparing events/year during the 24-week follow-up period compared to the 12 months prior to screening Population of interest: Severe refractory asthma patients in India with elevated eosinophils Key intercurrent events: Discontinuation of treatment (for any reason)
	 Strategy for intercurrent events: Treatment policy strategy will be used for treatment discontinuation. This will estimate the treatment effect over the 24 week study period regardless of treatment discontinuation.
	The remaining secondary estimands are defined by the following: Endpoints:
	• Change from baseline in clinic pre-bronchodilator FEV ₁ at week 24
	Change from baseline in clinic post- bronchodilator FEV ₁ at week 24
	 Change from baseline in ACQ-5 score at week 24 Change from baseline in morning PEF during weeks 20 - 24
	 Summary measure: Mean change from baseline in clinic prebronchodilator FEV₁ at week 24 Mean change from baseline in clinic postbronchodilator FEV₁ at week 24
	 Mean change from baseline in ACQ-5 score at week 24 Mean change from baseline from baseline in
	morning PEF during weeks 20 – 24 Population of interest: Severe refractory asthma nationts in India with
	 Severe refractory asthma patients in India with elevated eosinophils Key intercurrent events:
	Discontinuation of treatment (for any reason)

Objectives	Endpoints
	Strategy for intercurrent events:
	• Treatment policy strategy will be used for
	treatment discontinuation. This will estimate the
	treatment effect at the end of the 24 week study
	period regardless of treatment discontinuation.
Exploratory	

weeks to -1

week)

visit

4. STUDY DESIGN

4.1. **Overall Design**

This is a multi-centre, open-label, single arm 24-week study.

V1 V2* V3 V4 V5 V6 V7 V8 Mepolizumab 100 mg, SC-← -2 weeks → ← to -1 week W0W4 W8 W12 W16 W20 W24 Screening End of visit (-2 study

Treatment Period

V, visit; W, week; SC, subcutaneous

The primary estimand is the incidence of AEs, SAEs and AESIs in adult Indian participants with severe refractory asthma with elevated eosinophils while on-treatment with mepolizumab 100mg SC during a 24-week study.

^{*}All screening procedures will be performed at least -2 weeks to -1 week prior to first dose of mepolizumab at Visit 2 (Week 0). Screening visit would be at least 7 day prior to dosing visit.

4.1.1. Screening

Participants who meet all eligibility criteria at the Screening visit (Visit 1) will enter the study and asked to come to the clinic after at least 1 week for Visit 2 (Week 0).

Participants must understand and agree to use the study drugs for the treatment of asthma, or asthma exacerbation, for the duration of the study. OCS use and OCS dose adjustment in participants will be as per the investigator's discretion and clinical practice.

At Visit 1, the screening visit, the screening ACQ-5 score will be captured. Participants who meet study eligibility criteria, are eligible to enter the Treatment period. All screening procedures will be performed -2 weeks to -1 week (screening visit would be at least 7 day prior to dosing visit) before first dose of mepolizumab (Visit 2, Week 0).

The ACQ-5 questionnaire has been validated in several separate studies and the minimal clinically important difference value of +0.5 has been established to demonstrate a significant clinical change in asthma status (Juniper, 1999; Korn, 2011).

4.1.1.1. Exacerbation Management

Anytime during the study when a participant experiences an exacerbation the exacerbation should be treated according to the investigator's clinical practice.

4.1.2. Treatment period

At Visit 2 (Week 0), participants who meet the Treatment Period eligibility criteria will receive Mepolizumab 100mg SC every 4 weeks.

Subsequently, participants will continue to receive with mepolizumab 100mg SC every 4 weeks. During this period, participants will remain on their baseline asthma medications. OCS use and OCS dose adjustment in participants will be as per the investigator's discretion and clinical practice.

4.1.2.1. Exacerbation Management during Treatment Period

Anytime during the study when a participant experiences an exacerbation the exacerbation should be treated according to the investigator's clinical practice.

The participant will return for each subsequent Visit, to receive their subsequent doses of open label study treatment, as scheduled.

4.1.3. IP Discontinuation Visit

The IP discontinuation visit will be performed 4 weeks following the last dose of mepolizumab with a window of ± 7 days. Also, if a participant permanently stops study intervention, the participant is not required to withdraw from the study. Every effort should be made by the PI/staff to keep the subject in the study to collect important efficacy and safety data. In the event of discontinuation of study, the end of study visit activities should be performed as specified in SoA table (Section 1.3).

4.2. Scientific Rationale for Study Design

Though safety and efficacy of mepolizumab in patients with severe eosinophilic asthma has been established in various clinical studies across USA and Europe, this will be the first clinical study to assess safety in Indian patients.

Eosinophilic inflammation of the airways plays a central role in the pathogenesis of asthma (Seminario, 1994; Rothenberg, 1998; Wardlaw, 2000; Cohn, 2004). The overproduction of IL-5 has been specifically reported in patients with a variety of eosinophil associated disorders including asthma (Robinson, 1992; Sur, 1995). Mepolizumab binds with high specificity and affinity to human interleukin 5 (IL-5), the key cytokine responsible for regulation of blood and tissue eosinophils. A therapeutic strategy targeting IL-5 with mepolizumab represents a focused therapeutic option, which results in reduced eosinophil levels and important clinical benefits for patients with eosinophilic inflammation associated with severe asthma who are receiving optimised standard of care therapy.

There is significant unmet medical need to provide better treatment options in patients with severe eosinophilic asthma who need systemic corticosteroids for maintenance, given undesirable safety profile of OCS and the limited application of omalizumab in severe asthma (Normansell, 2014). In patients aged ≥12 years with severe eosinophilic asthma in the phase III studies, adding subcutaneous mepolizumab 100 mg q4w to current asthma therapy significantly reduced the rate of clinically relevant asthma exacerbations and significantly improved asthma control and had acceptable tolerability (with headache the most common adverse event). Further, the SIRIUS study demonstrated that in patients requiring daily oral glucocorticoid therapy to maintain asthma control, mepolizumab had a significant glucocorticoid-sparing effect. This study will also evaluate the OCS sparing effect in Indian patients with severe eosinophilic asthma (only to be assessed in patients who completed or withdrew from the study prior to the adoption of protocol amendment 4).

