1.2 Schema, 4.1 Overall Design	The schema has been updated with respect to the removal of OCS	Schema has been updated as OCS information is no longer required.		
1.3 Schedule of Activities (SoA)	SoA has been updated for the removal of information regarding OCS and associated phases.	OCS requirement has been removed to align with the current management practice of SEA which does not include use of stable OCS use for prolonged periods of time and the changes are in line with prescribing information of the product.		
	Stringency of spirometry timings	To allow flexibility for the patients		
	(i.e. must be performed at the same time ±1 hour of the visit 1) has been removed.	by broadening the time window for the spirometry within the day of the study visit.		

Section # and Name	Description of Change	Brief Rationale			
	Advisory statement for 12-Lead ECG has been added.	To maintain the uniformity across the protocol.			
	Serum IgE (total) - Serum IgE has been removed from week 24 and IP discontinuation visit	Assessment of change from baseline is not an objective or endpoint of the study			
3.0 Objectives and Endpoints		Only a subset of patients (those completing or withdrawn from the study prior to protocol amendment 4) will be assessed for this endpoint where a structured OCS tapering schedule was mandated within the previous study protocols and protocol amendments			
	Description of estimands have been added for all primary, secondary and exploratory endpoints	The rationale to add estimands is that estimands provide the precise description of what is being estimated for primary endpoints also explain about how to deal with intercurrent events which may occur during the study.			
5 Study Population 6 Study Intervention 8 Efficacy Assessments	Inclusion criteria 5 has been updated with respect to the removal of requirement for background systemic corticosteroids. Information regarding OCS phases has also been removed.	OCS requirement has been removed to align with the current management practice of SEA which does not include the use of a stable OCS dose for prolonged periods of time and the changes are in line with prescribing information of the product. Only a subset of patients (those completing or withdrawn from the study prior to protocol amendment 4) will now be assessed for the			

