4.4. End of Study Visit

A participant is considered to have completed study treatment if he/she has received a dose of mepolizumab at Visit 7 (Week 20) of the study.

A participant is considered to have completed the study if he/she has completed the 24 week treatment period of the study including the end of study visit.

The end of the study is defined as the date of the last visit of the last participant in the study.

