7.2. Participant Discontinuation/Withdrawal from the Study

Participants who permanently stop study intervention are not required to withdraw from the study. If for any reason a participant must permanently stop study intervention every effort should be made by the PI/staff to keep the subject in the study to collect important efficacy and safety data.

- A participant may withdraw from the study at any time at his/her own request or may be withdrawn at any time at the discretion of the investigator for safety, behavioural, compliance or administrative reasons. This is expected to be uncommon.
- At the time of discontinuing from the study, if possible, an end of study visit should be conducted, as shown in the SoA. See SoA for data to be collected at the

time of study discontinuation and end of study for any further evaluations that need to be completed.

- If the participant withdraws consent for disclosure of future information, the sponsor may retain and continue to use any data collected before such a withdrawal of consent.
- If a participant withdraws from the study, he/she may request destruction of any samples taken and not tested, and the investigator must document this in the site study records.
- Reasons for withdrawal must be captured in the eCRF and can include: an adverse
 event, lost to follow-up, protocol violation, lack of efficacy, sponsor terminated
 study, non-compliance, pregnancy, abnormal liver function test, abnormal
 laboratory results including clinically significant abnormality identified on ECG
 over-read.

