10. SUPPORTING DOCUMENTATION AND OPERATIONAL CONSIDERATIONS

10.1. Appendix 1: Regulatory, Ethical, and Study Oversight Considerations

10.1.1. Regulatory and Ethical Considerations

This study will be conducted in accordance with the protocol and with:

- Consensus ethical principles derived from international guidelines including the Declaration of Helsinki and Council for International Organizations of Medical Sciences (CIOMS) International Ethical Guidelines
- Applicable ICH Good Clinical Practice (GCP) Guidelines
- Applicable laws and regulations
- The protocol, protocol amendments, ICF, Investigator Brochure, and other relevant documents (e.g., advertisements) must be submitted to an IRB/IEC by the investigator and reviewed and approved by the IRB/IEC before the study is initiated.
- Any amendments to the protocol will require IEC/IRB approval before implementation of changes made to the study design, except for changes necessary to eliminate an immediate hazard to study participants.
- The investigator will be responsible for the following:
 - Providing written summaries of the status of the study to the IRB/IEC annually or more frequently in accordance with the requirements, policies, and procedures established by the IRB/EC
 - Notifying the IRB/IEC of SAE or other significant safety findings as required by IRB/IEC procedures
 - Providing oversight of the conduct of the study at the site and adherence to requirements of 21 CFR, ICH guidelines, the IRB/IEC, European regulation 536/2014 for clinical studies (if applicable), and all other applicable local regulations

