10.12. Appendix 12: Protocol Amendment History

The Protocol Amendment Summary of Changes Table for the current amendment is located directly before the Table of Contents (TOC).

Amendment 4 03-AUG-2022

Overall Rationale for the Amendment:

- i) The requirement of oral corticosteroids (OCS) and associated phases (Induction phase, optimization phase, OCS reduction/Manitenance phase) has been removed.
- ii) Inclusion criteria (S. no. 5) have been updated from the study to align with the current management practice of SEA which does not include use of stable OCS use for prolonged periods of time and the changes are in line with Prescribing information of the product.
- iii) Stringency of spirometry timings (i.e. must be performed at the same time ± 1 hour of the visit 1) has been removed.
- iv) The recommendation of triplicate 12-lead ECG within 4 minutes duration has been removed.
- v) The information for reporting SAE to GSK has been updated.

Amendment -3 17-MAR-2021

Overall Rationale for the Amendment:

i) As per recommendation by DCGI, Immunogenicity assessments have been added at Induction Phase, IP discontinuation Visit/End of Study Visit. Details of Immunogenicity testing provided

Amendment 2 05-NOV-2020

Overall Rationale for the Amendment:

- i) The time point for IgE (total) are updated and testing for IgE (specific) is removed.
- ii) The immunogenicity testing is no longer applicable for this study
- iii) Changes in the spirometry assessments are made.
- iv) Rescreened patients will be assigned a new screening number.
- v) The guidance to conduct the study during COVID-19 pandemic is added.

Amendment 1 27-AUG-2019

Overall Rationale for the Amendment:

- i) The sample size revised to 100 evaluable patients
- (ii) In the inclusion criteria, the age of the patients to be enrolled is \geq 18 years
- (iii) IgE levels evaluated before screening of patients

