APPENDIX 5. LIST OF TABLES, FIGURES AND LISTINGS

List of Tables

| Table | Table Title |
|-----------|--|
| Number | |
| 14.1.1.1 | Summary of Subject Disposition (Enrolled Population) |
| 14.1.1.2 | Summary of Reasons for Discontinuation (Safety Population) |
| 14.1.1.3 | Summary of Reasons for Screen or Run-in Failure (All Enrolled Population) |
| 14.1.1.4 | Summary of Inclusion, Exclusion and Induction Phase Criteria Deviations (Safety Population) |
| 14.1.1.5 | Summary of Important Protocol Deviations (Safety Population) |
| 14.1.1.6 | Summary of Important Protocol Deviations Leading to Exclusion to Treatment (Safety Population) |
| 14.1.1.7 | Summary of Important Protocol Deviations Related to COVID-19 Pandemic (Safety Population) |
| 14.1.1.8 | Summary of Visits Impacted by COVID-19 Pandemic (Safety Population) |
| 14.1.2.1 | Summary of Demographic Characteristics (Safety Population) |
| 14.1.2.2 | Summary of Asthma History and Baseline Disease Characteristics (Safety Population) |
| 14.1.2.3 | Summary of Asthma Exacerbation History (Safety Population) |
| 14.1.2.4 | Summary of Family History of Cardiovascular Risk Factors (Safety Population) |
| 14.1.2.5 | Summary of Medical Conditions (Safety Population) |
| 14.1.2.6 | Summary of Asthma Medications Taken by Treatment Period and Respiratory Medication Class |
| | (Safety Population) |
| 14.1.2.7 | Summary of Non-Asthma Concomitant Medications Taken During Treatment (Safety Population) |
| 14.1.2.8 | Summary of Screening, Run-in and Baseline Lung Function Results (Safety Population) |
| 14.1.3 | Summary of Treatment Exposure and Number of Study Drug Administration (Safety Population) |
| 14.2.1.1 | Analysis of Subject Achieved at least 50% Reduction in OCS Dose During Weeks 20-24 |
| 44.0.4.0 | Relative to Baseline, while Maintaining Asthma Control (Safety Population) |
| 14.2.1.2 | Summary of OCS Dose Categories During Weeks 20-24 (5 mg Cut-off) (Safety Population) |
| 14.2.1.3 | Summary of OCS Dose Category During Each Reporting Period (Safety Population) |
| 14.2.1.4 | Summary of Percent Change from Baseline OCS Dose Categories Relative to Baseline by Reporting Period (Safety Population) |
| 14.2.1.5 | Summary of OCS Dose (mg/day) and Change from Baseline During Each Reporting Period (Safety Population) |
| 14.2.1.6. | Summary of Median Percent OCS Dose (mg/day) Reduction During Weeks 20-24 While |
| | Maintaining Asthma Control (Safety Population) |

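### The OCS-sparing subset is chosen by exit status at Amendment 4, so it over-represents early withdrawals if anyone was on treatment at adoption, and the visible SAP tables do not carry the subset

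*Protocol*

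**What the plan says.** Protocol section 4.2 states that the study will also evaluate OCS sparing, "only to be assessed in patients who completed or withdrew from the study prior to the adoption of protocol amendment 4". The summary of changes at the front of the protocol corroborates this: "Only a subset of patients (those completing or withdrawn from the study prior to protocol amendment 4) will be assessed for this endpoint". It gives as the reason that this is the group "where a structured OCS tapering schedule was mandated within the previous study protocols and protocol amendments".

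Protocol section 4.4 counts a participant as having "completed the study if he/she has completed the 24 week treatment period of the study including the end of study visit".

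Adoption is not given as a single date. Protocol Appendix 12 has "Amendment 4 03-AUG-2022", SAP section 2 cites 23 August 2022, and Protocol section 10.1.1 says "Any amendments to the protocol will require IEC/IRB approval before implementation of changes made to the study design", so implementation may differ by site.

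On the analysis side, SAP section 7.2.5 defines the maintenance dose as the average daily dose over Weeks 20-24. SAP section 10.7 leaves missing values missing; its only visible OCS imputation is for participants with an exacerbation in Weeks 20-24. SAP section 12 takes participants with an observation as the default denominator. SAP Appendix 5 lists Table 14.2.1.1, "Analysis of Subject Achieved at least 50% Reduction in OCS Dose During Weeks 20-24", and the other OCS tables to 14.2.1.6, all on the Safety Population.

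**The concern.** Restricting the evaluation to the period when a taper was mandated is sensible. The difficulty is that membership depends on how and when a participant left the study, not on when treatment started. Participants first dosed well before adoption are all in, whether they completed or withdrew. Of those first dosed in the last 24 weeks or so, only the ones who had already withdrawn are in. This is selection by right truncation: the recent withdrawals are kept without the participants who stayed.

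At stake is whether the subset represents the patients treated under the taper schedule. Its withdrawal share would be too high, and dose summaries for the early reporting periods would include extra participants who were about to leave.

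**Working it through.** **The plan's own figures.** The documents give no size, accrual or withdrawal figure for this subset. The study's sample-size figures do reproduce: 100 / (1 − 0.35) = 153.8, so 154 screened; 1 − 0.98^100 = 0.8674, against 0.8673 printed. Neither is an input here.

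**Inputs.**
- From the documents: 24 weeks from first dose to completion (Protocol 4.4). On withdrawal, Protocol 7.2 says only "This is expected to be uncommon".
- Assumed: uniform accrual over A weeks before adoption, and a true 24-week withdrawal proportion d = 10%.

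**Step 1: withdrawals spread evenly over 24 weeks.** Count participants in weeks of accrual.
- First dosed more than 24 weeks before adoption: A − 24, all kept, of whom 0.1 × (A − 24) withdrew.
- First dosed within 24 weeks: someone dosed t weeks before adoption has already withdrawn with probability 0.1 × t/24. The average over t from 0 to 24 is 0.05, so 24 × 0.05 = 1.2 are kept, all of them withdrawals.
- Withdrawal share = [0.1 × (A − 24) + 1.2] / [(A − 24) + 1.2].

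| A (weeks) | Calculation | Share withdrawn |
|---|---|---|
| 40 | 2.8 / 17.2 | 16.3% |
| 52 | 4.0 / 29.2 | 13.7% |
| 78 | 6.6 / 55.2 | 12.0% |
| 104 | 9.2 / 81.2 | 11.3% |

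**Step 2: constant withdrawal hazard instead.** With λ = −ln(1 − d)/24, the average probability that a late entrant has already withdrawn is 1 − (1 − e^(−24λ))/(24λ), which is 0.0509 at d = 10%. The shares are 18.3% (A = 36), 13.8% (52), 12.0% (78), 11.4% (104) and 10.9% (150). For d from 5% to 20%, the shares run from 9.6% to 33.7% at A = 36 and from 5.7% to 22.4% at A = 104.

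**Step 3: in people, at d = 10% and constant hazard.**
- 30 early and 10 late entrants: subset 30 + 0.51 = 30.5; share (3 + 0.51)/30.5 = 11.5%.
- 20 early and 20 late: subset 20 + 1.02 = 21.0; share (2 + 1.02)/21.0 = 14.4%.
- 40 early and none late: 4/40 = 10%, no distortion.

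**Step 4: effect on the OCS outputs.** A participant who leaves before Week 20 has no Week 20-24 dose, stays missing and is outside the default denominator. The percentage with at least 50% reduction is then not directly changed. Such a participant does contribute to the reporting periods before leaving, which are summarised in Tables 14.2.1.3 to 14.2.1.5. The percentage would fall only if withdrawals were counted as failures. With an assumed 50% response in completers and the Step 1 shares, a true 0.5 × 0.90 = 45.0% would become 0.5 × (1 − 0.163) = 41.9% at A = 40, or 0.5 × (1 − 0.113) = 44.3% at A = 104.

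**Step 5: selection by first-dose date.** If only those first dosed at least 24 weeks before adoption are taken, and all of them are kept, the 1.2 disappears from both lines of the formula and the expected share is the true 10%.

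**The case against.** The strongest reply is that this is a sentence in a design rationale, not an analysis population. Neither Protocol section 9.3 nor SAP section 6 defines such a subset. SAP Appendix 5 puts the OCS tables on the Safety Population, and SAP section 2 says its differences supersede the protocol. On the visible text, then, the truncated group may never be analysed. The exploratory endpoint text is also largely missing from the public copies, so an operational definition could exist there and cannot be called absent. Finally, the excess is likely to be one or two people: about 5% of late entrants at 10% withdrawal, so 1 of 20 or 1.5 of 30.

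Most of this stands, and it limits the point. It does not remove it. If the restriction is applied as written, the selection follows whenever someone was on treatment at adoption. If it is not applied, the OCS tables include participants for whom no taper was mandated, contrary to section 4.2. Either way the group to be analysed needs one clear definition.

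A reader might infer that the rule biases the headline proportion with at least 50% reduction. The documents do not support that: it requires withdrawals to be counted as failures, which no visible text specifies, and the visible defaults point the other way.

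**Conclusion.** The rule in Protocol section 4.2 selects on exit status and over-represents early withdrawals if anyone was within about 24 weeks of first dose at adoption. The direction follows from the definition. The size cannot be found from the documents, which give no accrual dates, withdrawal rate or number on treatment at adoption. Under an assumed 10% withdrawal and uniform accrual over 40 to 104 weeks, the share is about 16% to 11%. It approaches 10% with longer accrual and equals 10% if nobody was on treatment. It would be wrong to conclude that the subset is certainly distorted, or that the SAP is set to analyse it.

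The consequence is confined to subset composition and the earlier-period dose summaries of an exploratory evaluation with no hypothesis test. The mismatch between the protocol's restriction and the SAP's Safety Population labels is visible on the page and needs reconciling in any case. This is a minor point, worth correcting because the correction is short.

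**What to change.** Define the OCS subset by date of first dose: all participants whose nominal Week 24 visit, taken as first dose plus 168 days plus the 7-day window (175 days), fell before Amendment 4 was implemented at their site, whether they completed or withdrew. Leave out everyone first dosed later, including their early withdrawals. If site implementation dates are not held, use one stated cut-off date for all sites. Put the definition in Protocol section 4.2 and the SAP, and label Tables 14.2.1.1 to 14.2.1.6 with this subset. State in the same place how withdrawals before Week 20 are counted.

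The cost is a sentence or two in each document and new table labels. A few late-entry withdrawals, and completers whose day 175 fell after the cut-off, leave the subset. The implementation dates must be obtained, since the documents do not show that they are in the study data.
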